6.4. Masking

The present study is considered blind to third parties; simple blinding due to logistics problems is not considered. Both the principal investigator and the nurses and subjects participating in the study know the method that will be applied to them. However, if it is considered blind to third parties, since the assessment of hemolysis is carried out by team personnel who are unaware of the method used in antebraichial venous cannulation for each sample analyzed.

6.5. Period of washing and follow-up

A washout period is foreseen between the intervention and the randomly assigned comparator for approximately one week. It will depend on the washout period of the clinical trial of bioequivalence. As a consequence, sufficient time is considered to eliminate the possible residual effect of topical heat and high pressure of the sphygmomanometer. Figure 1.

In the bibliography there is no indication of the time of the antegrade reflux in the upper limbs, so it has been adapted to what is indicated for the lower limbs in retrograde reflux, which is 0.5 seconds without muscle action (38). It has been estimated approximately 0.2 seconds since it is antegrade reflux with muscle action.

In the first instance, no follow-up period is foreseen, unless there is a secondary effect, which will continue until its cessation.

6.6. Justification of the design

It is considered that the methodology reflected in the present study could be justified under the following assumption well designed and correctly executed randomized clinical trials (RCTs) provide the best evidence on the effect of health interventions; according to the CONSORT guide (39,40).

All the "critical points" that this guide reflects throughout the present work have been addressed; in order to ensure that the information provided is sufficient and accurate (39,40).

Likewise, the study is supported by the extension of the guide that collects information adapted to clinical trials with non-pharmacological interventions; as is this case (40,41). To address the disparity of experience and skill of nurses is supported by the randomization of both interventions and the indistinct eligibility of the nurses participating in the present clinical trial (41).

Open study is justified by the difficulty of masking interventions. In the extension CONSORT for Trials Assessing Nonpharmacologic Treatments, it highlights the change in its item 11, masking, in what refers to semantics. In such a way that it introduces the possibility of directing the masking towards those collaborators who apply the interventions, instead of masking the interventions towards the subjects and in the evaluation of results (41).

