6.2. Design and comparator

Experimental, randomized and controlled study with the usual technique of inserting a venipuncture catheter until now. Incomplete clinical trial, blind to third parties, in healthy volunteers, which consists of three arms, in which they are intervened and the comparator is applied.

Three interventions are established and a common comparator for all of them. Interventions:

1. Application of dry topical heat.
2. Application of high stagnation pressure.

3. Application of dry topical heat and high stagnation pressure. That is, the combination of the previous two.

Comparator:

1. Usual clinical practice, until now

Therefore, all individuals will be subjected to one of the three interventions and the comparator, whose sequence corresponds to the two periods established by the clinical trial of bioequivalence.

Therefore, all individuals will be subjected to one of the three interventions and the comparator, whose sequence corresponds to the two periods established by the clinical trial of bioequivalence.

It is understood that it is a crossover clinical trial because each subject is exposed to an intervention, and it is their own control; it is exposed to the comparator, whose purpose is to reduce the intraindividual variability and accentuate the effectiveness of the intervention per se. It is an incomplete crossing because it is not possible to subject each individual to the three interventions and it must be only one per random assignment. This impossibility could be supported by the low frequency of clinical trials of four periods carried out in the accessible environment.

In this way, any of the interventions assigned to it can be compared with the current procedure for antebrachial venous cannulation

6.3. Random assignment of interventions.

The intervention and the sequence of application of the intervention with the comparator will be randomly assigned.

They will be assigned with sealed envelopes where inside the corresponding intervention to be applied, the comparator and the corresponding sequence will be detailed. Emerging the following options:

1. CA-> C. Topical first period heat. Comparator in the second period.
2. C-> CA. Comparator in the first period. Topical heat in the second period.
3. P-> C. High pressure in the first period. Comparator in the second period.
4. C-> P. Comparator in the first period. High pressure in the second period.

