13. PRACTICAL CONSIDERATIONS

13.1. Training of the nursing team and collaborators / observers

It is considered necessary to train the nursing team with certain scales that, except for the VAS / Numeric scale, are not commonly used in routine clinical practice. Likewise, interventions require specific knowledge a priori.

No training is contemplated, because the nurses are familiar with the material resources they will use, only a training is planned with the possibility of asking questions and these will be solved and / or clarified. The main researcher will belong to the collaborating nursing team and will support them in the fieldwork.

Similar situation is that of collaborators / observers of the intensity of hemolysis. Those involved in the evaluation of blood samples will be trained, although they are trained in the use of the material involved.

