14. STATISTICAL ANALYSIS PLAN

14.1. Main analysis

14.1. 1. Definition of variables

Primary variable

Successful venipuncture at the first attempt. Dichotomous qualitative variable. Success / Failure

Secondary variables

Successful venipuncture frequency. Discrete quantitative variable. (1,2,3,4)

Visual intensity of hemolysis. Discrete quantitative variable. It is measured in stadiums.

Scale of expressed pain intensity (VAS). Discrete quantitative variable.

Scale skin types Fitzpatrick. Discrete quantitative variable.

Ingestion of liquids (less than 500 ml) in the last 6-8h prior to cannulation. Discrete quantitative variable (measured in glasses); it will be transcribed continuously for statistical analysis.

Affiliation of individuals

Respected fasting of 6-8 hours. Dichotomous qualitative variable.

Age. Quantitative variable continues.

Sex. Dichotomous qualitative variable.

Race. Discrete quantitative variable. 1 -> Caucasian 2 -> Black 3 -> Asian 4 -> Latin

BP. Continuous quantitative variable.

HR. Continuous quantitative variable.

T. Continuous quantitative variable.

BMI Continuous quantitative variable.

14.1. 2. Sample size calculation

The sample calculation is performed with the GRANMO calculator (63). It assumes a random risk (alpha) of 5% and a statistical power (beta) of 80%; for which it is tried to prove the veracity of the null hypothesis, of bilateral type.

That is, the risk of rejecting the null hypothesis when this is true is 5%, and the probability of not rejecting it being false is 20%.

In the literature, the success of peripheral intravenous canals was recorded in the first attempt, using the usual technique, in 74% of the cases (55). Currently, a proportion of peripheral intravenous cannulation has been registered at the first attempt of 73%, in an ultrasound ecoguided manner (33). In relation to the second successful attempt, in the usual clinical practice it amounts to 92% of the cases and, in the ultrasound ecoguided to 91% (33.55).

For the present work we intend to achieve a 95% success rate in antebrachial venous cannulation at the first attempt. Thus, overcome with one of the alternative methods proposed in this study the cumulative proportion of the second attempt of the usual and eco guided clinical practice.

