It is considered a clinically relevant difference the successful venous cannulation at the first attempt when, not only allows the cannulation at the first attempt of those cases that hypothetically would be observed, but accumulate to those cases that, in a way observed in the literature, the cannulation has been achieved at the second attempt, and hypothetically, that success can be achieved in the first attempt.

The comparative indicators are based on the comparison method and the reduction of intraindividual variability. It is considered a root of the experience, one of them is lost; An average of both percentages has been made, thus obtaining a 12% loss approximately.

Therefore, the calculation of the sample size should be followed through the modality of proportions, paired measures (repeated in a group). Fix in the proportion with pre-intervention event 0.74, in the proportion with post-intervention event 0.95, and the loss ratio 0.12.

Finally, the estimated sample size is 60 subjects.

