14.1.3.1.2. MULTIVARIATE STATISTICS

Therefore, it is considered pertinent to perform a logistic regression, multivariate statistics. The primary variable is assumed as the dependent variable and the secondary variables as returnable or explanatory. The primary variable fulfills the requirement of being dichotomous and the return variables assume any type of variable. It is assumed the need to create dummy variables with alternative methods, whose reference will be the comparator.

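### The envelopes randomise method and order but not the nurse, so the own-control comparison is within subject but not within operator, and no listed variable would reveal an imbalance

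*Combined protocol and SAP*

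**What the plan says.** Table 1 (section 4.1.1) lists experience and skill among the factors that affect venipuncture. Section 6.6 takes up differences in skill between nurses and relies on "randomization of both interventions and the indistinct eligibility of the nurses participating in the present clinical trial".

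Section 6.2 calls the design a crossover because "each subject is exposed to an intervention, and it is their own control". Section 6.3 allocates the intervention and the order of intervention and comparator by sealed envelope. Each set of twelve holds two envelopes per order for each of the three interventions, and five sets are planned. There is one randomisation, in the first period, so the second-period method is known from then on.

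Section 6.4 leaves the investigator, nurses and subjects unmasked; only the hemolysis raters are blind. Section 13.1 adds: "The main researcher will belong to the collaborating nursing team and will support them in the fieldwork".

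On residual effects, section 6.5 plans a washout of about one week and states that "sufficient time is considered to eliminate the possible residual effect of topical heat and high pressure of the sphygmomanometer".

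The primary test is McNemar (14.1.3.1.1). A logistic regression on the secondary variables follows (14.1.3.1.2), with this coding: "It is assumed the need to create dummy variables with alternative methods, whose reference will be the comparator". Nurse, period and sequence appear neither in the variable list (14.1.1) nor in either analysis. The observers listed in 14.2.1 are hemolysis raters.

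**The concern.** First-attempt success depends on who holds the catheter, as the protocol itself recognises. Randomising the method balances subjects between methods. It does not assign nurses, and letting any nurse cannulate anyone neither balances nurses across methods nor keeps one nurse for a subject's two attempts. Pairing removes the subject's veins from the comparison but leaves the operator in.

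Because the method is known, and the second-period method is known in advance, nothing prevents a more skilled or more committed nurse from taking a larger share of the intervention attempts. If that happened, the false difference would favour the interventions, and the listed variables could neither show it nor adjust for it. The main objective is to find the best of three methods with about 18 to 20 subjects each (54/3 to 60/3), so a few points could matter to the ranking.

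A smaller point concerns period. The order is randomised, but the analysis never uses it.

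**Working it through.** **The plan's own figure.** Section 14.1.2 uses two-sided alpha 5% and power 80%, with these inputs: "Fix in the proportion with pre-intervention event 0.74, in the proportion with post-intervention event 0.95, and the loss ratio 0.12". The discordance is not given, so I assume independence within pairs:
- Discordant cells: 0.95 × 0.26 = 0.247 and 0.74 × 0.05 = 0.037, sum 0.284. Difference: 0.247 − 0.037 = 0.21.
- The normal approximation for McNemar gives 48.1 pairs. Adding 1/0.21 = 4.76 for continuity gives 52.9, and 52.9/0.88 ≈ 60.

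The stated 60 reproduces. This point does not dispute it; the 21-point difference is the yardstick below.

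**Operator.** Let g be the gap in success between a skilled nurse and the others, and let s_I and s_C be that nurse's shares of intervention and comparator attempts. With no method effect:

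false difference = g × (s_I − s_C)

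The documents give neither quantity, so both are assumptions:
- g = 10 points, share difference 0.2: 10 × 0.2 = 2.0 points.
- g = 20 points, share difference 0.3: 20 × 0.3 = 6.0 points.
- Share difference 0: bias 0 for any g.

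A simulation of 54 pairs (20,000 replicates, no method effect) agrees:

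| Nurse assignment | False difference (points) | Type I error, asymptotic McNemar |
|---|---|---|
| Unrelated to method (nurse SD 0.5 to 1.0 on the logit scale) | 0 | 5.0% to 5.2% |
| Skilled nurse (85% to 90% v 74%) does 60% of intervention, 40% of comparator attempts | 2.2 to 3.1 | 5.8% to 6.8% |
| Same nurse does 70% and 30% | 4.4 to 6.5 | 8.7% to 13.8% |

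In the last row, exact McNemar gives 5.5% to 9.3%, against 3.0% with no nurse effect. For scale, one success among 18 subjects is 1/18 = 5.6 points.

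**Period.** Let π be a common gain in success from period 1 to period 2. Intervention-first subjects contribute a within-subject difference shifted by −π, and comparator-first subjects one shifted by +π. With n1 and n2 subjects in the two orders, the bias has size:

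|n1 − n2| / (n1 + n2) × π

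- Balanced orders: 0. In simulation, with success rising from 74% to 88%, the bias is 0.0 points and asymptotic type I error is 4.2%.
- Ceiling: five sets × two envelopes = 10 subjects per order per intervention.
- Stopping at subject 54 (section 9.9), with no losses: four full sets give 8 per order per intervention, and six further envelopes add at most 2 to any one order. So 10 v 8 is possible within an intervention. With π = 10 (assumed): 2/18 × 10 = 1.1 points.
- With two losses from the shorter order as well, 10 v 6: 4/16 × 10 = 2.5 points.
- All interventions together, the worst split at 54 without losses is 30 v 24. With π = 14 points: 6/54 × 14 = 1.6, against 1.5 simulated.

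Section 7.4 can also unbalance the orders. The analysis is per protocol, and a subject who cannot be catheterised in period 1 is lost while the same failure in period 2 is kept.

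**Room for adjustment.** At 74% and 95% success, 54 pairs give 54 × 0.26 + 54 × 0.05 ≈ 17 failures, and about 54 × 0.284 ≈ 15 discordant pairs under independence. That will not support many extra model terms.

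**The case against.** The operator bias is conditional and its inputs are assumed. The documents give no roster, no skill gap and no indication that better nurses would do more intervention attempts. If any eligible nurse cannulates without regard to method, which is presumably the aim of section 6.6, there is no bias. Even 6 points is well short of 21. The method is also standardised: a step-by-step comparator guide (8.3), preset heating and a timer (8.5), unit procedures (12.1.3) and briefing of the nurses (13.1). All of this stands. But standardising the method does not equalise skill, and an intention that nurses be interchangeable is not an allocation. The case report form is not reproduced, so a nurse field may exist. What can be said is that no listed variable is one.

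Three stronger readings are tempting.
- A reader might infer that the main researcher will do most intervention attempts and so confound the result. Section 13.1 says only that this person joins the team and supports it.
- A reader might infer that leaving period out of the model mixes it with the method effect. It does not while the orders are balanced. Assessing VIA eligibility only at the first assessment shifts both orders alike and cancels in the same way.
- A reader might infer that an earlier catheter, a haematoma or knowledge of the vein biases the result. These distort the contrast beyond a common period shift only if they differ by the method given first. Section 9.8 speaks of haematoma lasting days, and section 6.5 plans about a week.

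**Conclusion.** The operator point holds as an unguarded risk, not as a demonstrated bias. Section 6.6 credits randomisation with handling nurse skill, but nurse is not randomised, fixed in advance or listed as a variable, and the trial is open. The bias is zero if nurse and method are unrelated. It is about 2 to 6 points if the skill gap is 10 to 20 points and a skilled nurse's share of attempts differs by 20 to 30 points between intervention and comparator. Both ranges are assumptions.

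Period is secondary. The balanced order removes a common period effect, and only lost balance lets it back in: about 1.1 points at 10 v 8 and 2.5 at 10 v 6 within an intervention, for an assumed 10-point effect.

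Neither part overturns the design or the sample size. The change is worth making because it is cheap and because nurse identity not captured at the attempt may not be recoverable later.

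**What to change.** 1. Sections 6.3 and 6.6: fix the nurse-to-chair list for each group of twelve before any envelope is opened, and use the same nurse for a subject's second period whenever that nurse is rostered.
2. Section 14.1.1: add a nurse code for each attempt.
3. Section 14.1.3.1: beside McNemar, report a period-adjusted paired analysis that uses the randomised sequence (Mainland-Gart, which compares discordant pairs between the two orders), in exact form given about 15 discordant pairs. Treat nurse only as a simple sensitivity analysis, for example a table of attempts by nurse and method and a repeat of the paired comparison in subjects who had the same nurse twice. With about 17 failures expected, do not load nurse terms into the main model.

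State in the plan that neither a period term nor Mainland-Gart corrects carryover that differs by the method given first; for that the trial relies on the washout.

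Cost: a roster sheet, one data field and one additional test, with no change to sample size or interventions. The downside is slightly less flexibility in who cannulates whom on the morning.

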7. SELECTION AND WITHDRAWAL OF SUBJECTS

7.1. Sampling and type of population

It is considered a non-probabilistic sample study, for the convenience of healthy volunteers. The existence of the bioequivalence test is communicated and it is the volunteers who come to register their participation for particular reasons, they are easily accessible groups with specific characteristics. In addition, all of them maintain a fast of, at least, 6-8 hours prior to peripheral intravenous cannulation.

All individuals recruited to perform the fieldwork must have met all the inclusion criteria, and none of exclusion.

7.2. Inclusion criteria.

Subjects that meet the following requirements will be included:

- o Age 18 to 55 years old (42).
- o Have signed the informed consent of this essay.

o Participate in a clinical bioequivalence trial of the Clinical Trials Unit of the University Hospital of La Princesa.

o Do not reach stage I on the VIA scale, in the first assessment.

o Fluid intake equal to or less than 500 ml, in the last 6-8 hours before venous drainage (15,38).

The exclusion criterion of VIA stage I scale could be justified as a consequence of the conclusions of the research study that precedes the present one (37).

7.3. Exclusion criteria

The default exclusion criteria:

o Carrier of a recognized or diagnosed disease. o Reach stage I on the VIA scale, in the first assessment.

o Ingestion greater than 500 ml of fluids in the last 6-8 hours before venous drainage (15,38).

o Not demonstrate the ability to understand the information sheet, and adhere to the instructions described.

7.4. Criterion of withdrawal and final data matrix

The data will be included in the final matrix for the analysis to those who have complied with the guidelines throughout the field work; in accordance with exclusion criteria. The following lost data are considered:

- No possibility of intravenous catheterization in the first period of the bioequivalence study.
- Subject that does not attend the second period.
-

It is not considered lost data when in the second period an intravenous cannulation is not possible but it has been tried at least once. It is possible to collect all the data required by this study for analysis of the primary variable; which is for which the individuals calculated in the sample size are required.

That is, only the data not lost or deviations from the protocol will be included; analysis for protocol compliance

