LOW LEVEL INTERVENTION CLINICAL TRIAL. A clinical trial that meets all of the following conditions: 1. The investigational drugs are used in accordance with the terms of the marketing authorization, or 2. the use of the investigational drugs is based on evidence and is supported by data published scientists on the safety and efficacy of such investigational medicinal products in one of the Member States involved. 3.⁹ The complementary diagnostic or monitoring procedures involve a risk or additional burden for the safety of the subjects that is minimal compared with that of the usual clinical practice in any of the Member States involved.

OPTIMAL POINT OF PUNCTURE. The one that presents adequate conditions in resistance to rupture, elasticity to palpation and free venous trajectory from distal to proximal in the case of puncture for intravenous injection.

PARESTHESIA. Numbness and tingling produced by pathology oppression in the nervous or circulatory system

PROTOCOL DEVIATION. Changes to the protocol without prior agreement

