8.3. Description of the comparator

Usual practice, up to now: The steps established in the standardized and approved venipuncture guide CLSI GP41-A6 (44) have been followed. It has been taken into account, the modification of said guide by Lima-Oliveira et al. in the order of steps to follow to put on the gloves; in such a way that it adapts to the usual clinical practice in Spain (27).

Therefore, the steps of the latter, CLSI GP41-A6 (44), will be followed, allowing the gloves to be placed in the order considered by the nurses. The irrevocable condition will be to comply with this step, as well as to comply before the step corresponding to the venipuncture itself.

The usual method does not involve the application of topical heat previously, and the tourniquet corresponds to latex.

In this protocol, venipuncture will refer to the insertion of peripheral intravenous catheter, from the caudal to the cranial part of the forearm. It will be considered successful, after the insertion of the catheter, venous reflux occurs and the extraction of a basal blood sample is possible.

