8.5. Adherence to interventions and protocol deviations

Adherence to the protocol will be ensured with the following resources:

- The time and the power of the heat source emitted to the carob bean sacks will be carried out by means of a microwave, whose power and time will be pre-set.

- The application time of the seed bags, seven minutes, will be controlled through a portable countdown timer. There will be a countdown and ascending timer with CE marking, for each subject. The nurse will program the device so that, after seven minutes from the application of the bags, an alarm is issued to remove them. Likewise, when the alarm sounds, an ascending count begins and the time elapsed in excess can be known; in which case.

Deviations from the protocol and data retrieved will be considered in the following cases:

Application of dry topical heat

1. If the two sacks of seeds are not heated sufficiently -> It will proceed to heat two more again. There will always be two more sacks of reserve; so reheating sacks is not recommended because the temperature that could reach them is unknown and could generate "noise" to assess the effectiveness of the intervention.
2. If 7 minutes are not reached -> Protocol deviation
3. If the bags are left in excess of 7 minutes -> Protocol deviation
4. If a sack of seeds is released, or both, and recovers to its previous position in less than 1 minute (Flexibility time). No need to let act one more minute -> Data recovered.
5. If a sack of seeds, or both, comes off and does not recover to its previous position in less than 1 minute (Flexibility time) -> Protocol deviation
6. If the two sacks of seeds were detached, without the possibility of estimating the time that has elapsed approximately -> It is recovered and the process is started again.

There will be another pair of bags for the possibility of loss of them.

Application of high tourniquet pressure

1. Pressure exerted with the sphygmomanometer less than 100 mmHg is considered insufficient -> Protocol deviation
2. If the pressure of the sphygmomanometer gradually decreases due to forgetfulness of the valve fixing that controls the air output before performing venipuncture-> fix the valve. Data recovered.
3. If the pressure of the sphygmomanometer gradually decreases due to forgetfulness of the valve fixing that controls the air output after performing venipuncture-> Protocol deviation

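### Section 7.4 makes a per-protocol set the only analysis in an open-label trial whose listed deviations concern heat and cuff pressure only; the differing non-cannulation rules for the two periods are a lesser point

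*Combined protocol and SAP*

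**What the plan says.** Section 7.4 lists two kinds of lost data. One is non-attendance at period 2. The other is "No possibility of intravenous catheterization in the first period of the bioequivalence study", with nothing said about whether a puncture was attempted. For period 2 it says that data are not lost "when in the second period an intravenous cannulation is not possible but it has been tried at least once", because the primary variable can then still be collected. It closes: "only the data not lost or deviations from the protocol will be included; analysis for protocol compliance". The grammar is loose, but the last words make the intent plain: deviators are excluded and the analysis is per protocol. Sections 14.1.3 and 14.3 define no other analysis set.

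Section 8.5 introduces its list with "Deviations from the protocol and data retrieved will be considered in the following cases" and then gives six items for dry heat and three for cuff pressure. Some items recover the data and others exclude it. None concerns the comparator. Comparator deviations are nonetheless possible: the Glossary has a general definition ("PROTOCOL DEVIATION. Changes to the protocol without prior agreement"), and section 8.3 attaches a firm requirement to the glove step ("The irrevocable condition will be to comply with this step").

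Section 6.4 states that the investigator, nurses and subjects all know the method. The primary variable is success or failure at the first attempt (14.1.1), and the primary test is McNemar (14.1.3.1.1).

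**The concern.** In a McNemar analysis an excluded deviation removes the subject's whole pair. Because the listed deviations all arise in the delivery of heat or cuff pressure, whether a pair survives depends on how the intervention period went, as judged by unblinded staff. This is harmless if deviators have the same success as everyone else. If they fail more often with the intervention than with the comparator, removing them raises the intervention rate more than the comparator rate and produces a gain that the method did not cause. With no other analysis set planned, a reader of the results could not tell which case applied.

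The period rules raise a smaller version of the same question. A subject who was punctured in period 1 and never cannulated has an observed first-attempt failure, just as in period 2. Read literally, 7.4 deletes that failure in one period and keeps it in the other.

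**Working it through.** **The plan's own figure.** Section 14.1.2 uses 0.74 versus 0.95, paired, two-sided 5%, power 80% and 12% loss. Take d = 0.21 and discordance pd = 0.26 + 0.05 = 0.31. Then n = [1.96·√0.31 + 0.84·√(0.31 − 0.21²)]² / 0.21² = 52.75, and 52.75 / 0.88 = 59.9. The stated 60 is reproduced and is not in dispute.

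**Excluding deviators when there is no true effect.** True success is set at 74% under both methods. A fraction f of pairs is dropped as deviators. Those subjects succeed with probability s under the intervention and 74% under the comparator. The retained intervention rate is (0.74 − f·s)/(1 − f), and the retained comparator rate stays at 74%. Both f and s are assumptions, because the documents give neither. Rejection rates come from full enumeration of McNemar with independent periods.

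*Cuff arms only, f = 0.05.* The sample size in 2.13 is 54, so 18 pairs per arm and 36 in the two arms that use the cuff. The number dropped is 36 × 0.05 = 1.8, leaving 52.2 pairs (52 used). At s = 0 the cuff-arm rate is 0.74/0.95 = 0.7789, a gain of 3.9 points. Pooled over all arms the gain is 36 × 0.05 × (0.74 − s) / 52.2, which at s = 0 is 1.332/52.2 = 0.0255.

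*All arms, f = 0.10.* The number retained is 54 × 0.9 = 48.6 (48 used). At s = 0 the rate is 0.74/0.90 = 0.8222, a gain of 8.2 points. This case also assumes a link between heat deviations and the result.

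| Deviators' success with intervention | Cuff 5%: gain in cuff arm / pooled (points) | McNemar uncorrected / exact | All arms 10%: gain (points) | McNemar uncorrected / exact |
|---|---|---|---|---|
| 74% | 0 / 0 | 5.3% / 3.0% | 0 | 5.2% / 3.0% |
| 50% | 1.3 / 0.83 | 5.4% / 3.0% | 2.7 | 6.1% / 3.7% |
| 25% | 2.6 / 1.69 | 5.7% / 3.3% | 5.4 | 9.6% / 6.2% |
| 0% | 3.9 / 2.55 | 6.3% / 3.7% | 8.2 | 16.0% / 11.0% |

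The gain shrinks if deviators also do worse on the comparator. With f = 0.10 and s = 25%, it is 0.10 × (c − 0.25)/0.90, where c is their comparator success. That gives 5.4 / 3.9 / 2.8 / 0 points for c = 74 / 60 / 50 / 25%.

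**The period 1 rule, read literally.** Section 14.1.2 gives 74% success at attempt 1 and 92% by attempt 2 for usual practice, and a 95% target. Success at attempt 2 after a failure is (0.92 − 0.74)/0.26 = 0.692, so failure is 0.308. This is assumed to hold at every later attempt. After k attempts the never-cannulated share is Lc = 0.26 × 0.308^(k−1) on the comparator, and Li lies between 0 and 0.05 × 0.308^(k−1) on the intervention. Section 6.3 puts 30 subjects in each order.

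For k = 4, matching the 1-4 coding in 14.1.1:
- Lc = 0.76% and Li = 0 to 0.15%.
- Subjects deleted: 30 × (Lc + Li) = 0.2 to 0.3 of 60.
- With D = 1 − (Lc + Li)/2 and independent periods, the comparator rate is 0.74 × (1 − Li/2)/D = 74.3%, and the intervention rate is 0.95 × (1 − Lc/2)/D = 95.0 to 95.1%.
- The difference moves from 21.0 to 20.7-20.8 points.

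For three attempts, 0.7 to 0.9 subjects are deleted and the difference is 20.1 to 20.3. For two attempts, 2.4 to 2.9 are deleted and it is 17.9 to 18.7, but no section sets a two-attempt limit and the 1-4 coding speaks against one.

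**The case against.** **On deviations.** Section 8.5 concerns adherence to the interventions, which have minutes and millimetres of mercury to measure. The comparator has no heat step, and 8.1.1 says that elastic-tourniquet pressure cannot be monitored, so an unequal list is natural. Several items recover data. Whole pairs are dropped, so comparator results are not selectively kept. All of this stands. A reader might infer that the plan is shown to favour the interventions; the documents do not support that. They give no deviation rate and no link between deviation and result. The 16% figure needs 10% deviation in every arm, no successes among deviators, and ordinary success for the same people on the comparator. In the cuff-only 5% case the exact test never exceeds its nominal level. What remains is that the mechanism can favour the intervention and no planned analysis would reveal it.

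**On period 1.** The wording may mean only subjects who were never attempted. There is also a practical reason for the rule. Section 9.2 places medication after cannulation, so a subject not cannulated may have no period 2 and hence no McNemar pair; this is an inference, since the plan does not say so. A reader might take the rule to delete all first-attempt failures, or to inflate the treatment difference. Neither follows. Section 9.4 records later success with its attempt number, so those subjects stay, and under the rates assumed here the deletion shrinks the difference. The practical reason explains absence from McNemar, but not removal of an observed result from the frequencies in 14.1.3.2.1.

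**On the cuff rule.** Section 8.5 classes as a deviation pressure lost through "forgetfulness of the valve fixing that controls the air output after performing venipuncture-> Protocol deviation", while 8.3 counts success once "venous reflux occurs and the extraction of a basal blood sample is possible". A reader might see a contradiction. There is none: the wording may refer to the time after the puncture is complete. It needs clarifying only.

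**Conclusion.** The concern holds for the analysis set and should be fixed. A per-protocol set is the only planned analysis, in an open-label trial where the listed deviations all depend on how the intervention was delivered. Bias arises only if deviators do worse with the intervention than with the comparator. Under the assumed rates, the spurious gain with no true effect runs from 0 to 3.9 points in a cuff arm (5% dropped, cuff arms only) and from 0 to 8.2 points (10% dropped, every arm). The top values need 0% success among deviators. These are illustrations, not estimates.

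The unequal treatment of non-cannulation in 7.4 is real as written but minor: a fraction of one subject in 60 and at most 0.3 point on the difference under the 1-4 coding. It rests on the literal reading and on the 74% and 92% rates, which the plan takes from outside studies and which may not fit healthy volunteers.

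**What to change.** In 7.4 and 14.1.3:

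- **(a) Analysis set.** Keep deviators and analyse by assigned method in the primary analysis, with McNemar on all complete pairs. Report the per-protocol set as a sensitivity analysis. Tabulate deviations by method, including the comparator, and by first-attempt result.
- **(b) One rule for both periods.** An attempted but unsuccessful cannulation is a first-attempt failure, and a period never attempted is missing. Add a "not achieved" code to the attempts variable, which now runs from 1 to 4. Subjects with period 1 only enter the frequencies of 14.1.3.2.1 but not McNemar.
- **(c) Clarification.** Reconcile the 8.5 item on pressure lost after the puncture with the success definition in 8.3.

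The cost is SAP wording, one code on the form and one extra table. First-attempt success or failure is already recorded (9.4), and the McNemar test and the 60 subjects stay. The price is that the primary estimate then includes imperfect delivery of the interventions. McNemar still cannot use a subject who has no second period.
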